## 4.0 Statistical Analysis

**D.1. Sample Size Calculation.** This pilot study is based on a convenience sample of 20 subjects per arm.

### D.2. Data Analysis

**Primary Objective:** Our primary objective is to determine the completion rate for patients enrolling in this study. Patients who complete the dyspnea NRS on day 72 will be counted as successes. Dropouts are defined as subjects who do not complete the dyspnea NRS on day 7 +/- 2, and will be counted as failures toward the feasibility outcome. We will declare the study as feasible if we observe at least 20 successes, based on a recent review of Supportive Oncology studies in our department in which we found that approximately 50% patients completed their interventional clinical trial.

**Objective #2.** We will test our hypothesis that 4 days of dexamethasone will improve dyspnea, respiratory function and quality of life for cancer patients using paired t-tests.

**Objective #3.** We will test our hypothesis that 7 days of dexamethasone will improve dyspnea, respiratory function and quality of life for cancer patients using paired t-tests. A sample size of 20 per arm will allow us to detect an effect size of 0.9 in the change of dyspnea NRS between baseline and day 7 with an 80% power and an alpha of 5%, assuming a standard deviation of 2.

**Objective #4.** We will test our hypothesis that dexamethasone will improve dyspnea, respiratory function and quality of life for cancer patients compared to placebo using two-sample t-tests on the differences between baseline and 4 and 7 days for each outcome measure.

**Objective #5.** We will test our hypothesis that increased dose results in better outcomes by comparing the first 7 days of treatment arm to the last seven days of the placebo arm. We will use two-sample t-tests on the differences between baseline (day 0 for treatment arm, day 7 for placebo arm) and 7 days later (day 7 for treatment arm, day 14 for placebo arm).

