**1.0 Objectives**

**A. Objectives**

**A.1. Primary Objective.** To determine the feasibility of conducting a randomized controlled trial (blinded phase) on dexamethasone in cancer patients with dyspnea. Our working hypothesis is that at least 50% of patients will complete the dyspnea numeric rating scale (NRS) on day 7+/-2.

**A.2. Objective #2.** To compare the intensity of dyspnea (NRS), forced expiratory volume (FEV1) and quality of life in cancer patients between baseline and after 4 days of dexamethasone use. Our *working hypothesis* is that 4 days of dexamethasone will improve dyspnea, respiratory function and quality of life for cancer patients.

**A.3. Objective #3.** To compare the intensity of dyspnea (NRS, cancer dyspnea scale), FEV1, and quality of life in cancer patients between baseline and after 7 days of dexamethasone use. Our *working hypothesis* is that 7 days of dexamethasone will improve dyspnea, respiratory function and quality of life for cancer patients.

**A.4. Objective #4.** To compare the intensity of dyspnea (NRS, cancer dyspnea scale), FEV1, in cancer patients between the dexamethasone arm and the placebo arm at 4 and 7 days. Our *working hypothesis* is that dexamethasone will improve dyspnea, and respiratory function for cancer patients compared to placebo.

**A.5. Objective #5.** To compare the intensity of dyspnea (NRS, cancer dyspnea scale), FEV1, and quality of life in cancer patients after 7 days of dexamethasone between the dexamethasone arm (8mg BID for 4 days followed by 4mg BID for 3 days) and the placebo arm (4mg BID for 7 days during the open label phase). Our *working hypothesis* is that a higher dose of dexamethasone will improve dyspnea, respiratory function and quality of life for cancer patients compared the lower dose.

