### 3.0 Experimental Approach

**C.1. Overall Study design.** This is a 2-arm, double blind, parallel randomized controlled trial of dexamethasone and placebo for cancer patients with dyspnea (Figure 1). The main goal of this study is to determine the effect size for both dexamethasone and placebo arm to inform a larger, adequately powered confirmatory randomized controlled trial. For this preliminary study, we plan to enroll 20 patients per arm, with a total of 40 patients for the entire study (see statistical considerations for more details). Patients will be randomized to either dexamethasone or placebo for 7 days in a blinded fashion; this will be followed by an open label phase in which patients in both arms would take dexamethasone for 7 days. The rationale for the open label phase is to give all patients an opportunity to try the study medication, and to examine the use of dexamethasone at a different dose as an exploratory endpoint (objective #5). Based on our experience conducting symptom control trials, we believe this study design is feasible and would not add undue burden for patients. To reimburse patients for their time and effort, we will provide a gift card for \$20 per visit (day 7+/-2 and day 14+/-2).

**C.2. Eligibility Criteria.** The eligibility criteria are shown in Table 2.

Table 2. Study Eligibility Criteria

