Dexamethasone is commonly used in oncology practice for management of cerebral edema, spinal cord compression, chemotherapy induced nausea and vomiting, bowel obstruction, pain, anorexia, dyspnea and fatigue. For patients with chronic obstructive pulmonary diseases, systemic corticosteroids have been clearly shown to reduce respiratory symptoms, improve FEV1 and shorten hospitalization in acute exacerbations (Falk et al. 2008, Walters et al. 2009, Wood-Baker et al. 2007). Furthermore, inhaled steroids have been demonstrated to improve various clinical outcomes in COPD patients including the number of physician visits and airway hyperreactivity (Calverley et al. 2007, Lung Health Study Research 2000, Yang et al. 2007). However, the efficacy of corticosteroids for dyspnea has not been clearly elucidated in cancer patients.

Our study proposes to use oral dexamethasone for the management of dyspnea. The dose of dexamethasone we plan to use is 8mg PO BID for 4 days, then 4 mg PO BID x10 more days. This is similar to doses we use for CINV prophylaxis (8-20mg IV/PO prior to chemotherapy, then 4-8mg q12h for up to 4 days after chemotherapy) (Mullin and Beckwith, [www.ifvrh.com/policies\\_quick\\_ref/Treatment\\_of\\_CINV.html](http://www.ifvrh.com/policies_quick_ref/Treatment_of_CINV.html)). This study is purely exploratory in nature, and we do not plan to seek FDA approval for the new indication of dyspnea.

The control arm will receive placebo capsules prepared by a compounding pharmacy (Green Park Compounding Pharmacy) identical in appearance to dexamethasone 4 mg capsules, and will be instructed to take two capsules twice a day for 4 days, followed by one capsule twice a day for 3 days.

In the open label phase, patients assigned to either arm will be asked to take dexamethasone 4 mg orally twice a day for 7 days. Both dexamethasone and placebo capsules used throughout this study will be compounded by Green Park Compounding Pharmacy and dispensed by Investigational Pharmacy at MD Anderson. Dexamethasone/placebo capsules will be provided free of charge to patients during the 14 day study period.

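### If 2 is the SD of the change, the 80% power stated for Objective #3 does not follow for its paired t-test; the sentence leaves the unit, the type of SD and the sidedness open

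*Combined protocol and SAP*

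**What the plan says.** The only power statement in the plan is in section D.2, under Objective #3. It reads "A sample size of 20 per arm will allow us to detect an effect size of 0.9 in the change of dyspnea NRS". The change in question runs from the baseline visit to the day-7 visit, and the remaining inputs are given as "with an 80% power and an alpha of 5%, assuming a standard deviation of 2". The only test named under that objective is the paired t-test. Section A.3 frames the objective as a within-patient comparison, "in cancer patients between baseline and after 7 days of dexamethasone use".

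Objective #4, the randomised comparison of dexamethasone with placebo, is to be analysed "using two-sample t-tests on the differences between baseline and 4 and 7 days for each outcome measure". It has no power statement.

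Three other places bear on how much this matters:
- Section D.1: "This pilot study is based on a convenience sample of 20 subjects per arm".
- Section D.2, Primary Objective: "We will declare the study as feasible if we observe at least 20 successes".
- Section C.1: "The main goal of this study is to determine the effect size for both dexamethasone and placebo arm", to inform a larger trial.

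**The concern.** The power sentence leaves three things open: whether 0.9 is in SD units or NRS points, whether 2 is the SD of the change or of a score at one visit, and whether the 5% is one- or two-sided. Because the sentence speaks of an effect in the change, the natural reading is that 2 is the SD of the change. On that reading 80% is not the power of a paired t-test with 20 patients, whichever unit 0.9 is in.

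A reader therefore cannot tell which comparison has 80% power or for what size of effect. That is awkward in a pilot meant to supply effect sizes for a confirmatory trial, since the plan's one numerical effect size has no unit.

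**Working it through.** **Inputs** (D.2, Objective #3): n = 20 per arm, effect size 0.9, SD 2, alpha 5%, stated power 80%. Sidedness is not stated; two-sided is assumed unless noted.

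**Formulas** (exact noncentral t, d = effect divided by the SD of the change):
- Paired: noncentrality d√n, df = n − 1.
- Two-sample: noncentrality d√(n/2), df = 2n − 2, with n per arm.

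**1. The plan's figure for its named test, with 2 as the SD of the change**
- 0.9 in SD units: d = 0.9, noncentrality 0.9 × √20 = 4.02, power 96.8% (98.7% one-sided). Twelve pairs already give 81%.
- 0.9 in NRS points: d = 0.9/2 = 0.45, noncentrality 0.45 × √20 = 2.01, power 48.0% (61.6% one-sided). Reaching 80% two-sided would need 41 pairs.
- Detectable at 80% power, two-sided: d = 0.660, which is 0.660 × 2 = 1.32 points.

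Neither unit and neither sidedness gives 80%.

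**2. Paired readings that do give about 80%**

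If 2 is a single-visit SD, the SD of the change is 2√(2(1 − r)), where r is the baseline-to-day-7 correlation. The documents give no r, so the values below are illustrative (n = 20, two-sided).

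| r | SD of change | Power, 0.9 points | Power, 1.8 points (0.9 × 2) |
|---|---|---|---|
| 0 | 2.83 | 27% | 77% |
| 0.10 | 2.68 | 30% | 81% |
| 0.50 | 2.00 | 48% | 97% |
| 0.70 | 1.55 | 69% | >99% |
| 0.77 | 1.36 | 80% | >99% |
| 0.80 | 1.26 | 85% | >99% |

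Setting effect/SD of change = 0.660 and solving gives r = 1 − (effect/0.660)²/8. This is about 0.77 for 0.9 points and about 0.07 for 1.8 points. One-sided, 0.9 points reaches 80.5% at r = 0.70.

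Pooling all 40 patients, with an SD of change of 2 and 0.9 points, gives noncentrality 0.45 × √40 = 2.85 and power 79.3%. Pooling is conceivable because in the open-label phase "patients assigned to either arm will be asked to take dexamethasone 4 mg orally twice a day for 7 days". But the sentence says 20 per arm and day 7, and at day 7 the control arm has taken only placebo.

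**3. The two-sample test of Objective #4, 20 per arm, SD of change 2**
- 0.9 SD: noncentrality 0.9 × √10 = 2.85, power 79.2% (81.2% by normal approximation). Detectable effect 0.909 SD, or 0.909 × 2 = 1.82 points.
- One-sided: 87.5%.
- 0.9 points (d = 0.45): 28.4%.

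The match to Objective #4 therefore needs 0.9 to be standardised and alpha to be two-sided. It is not unique. The pooled paired test has the same noncentrality, and so does a paired test with a single-visit SD and r = 0: 1.8/(2√2) × √20 = 2.85.

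**The case against.** The strongest reply is that the sentence is incomplete rather than wrong. Some readings make 80% correct for the paired test. And if 0.9 is in units of the SD of the change, 20 patients detect it with well over 80% power, so the claim errs on the safe side. The sample size does not rest on this calculation, and the only decision rule concerns feasibility.

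Much of this stands, and it keeps the point minor. It does not remove it. Each paired reading that gives 80% needs a correlation or a pooling rule that the plan does not state, and the natural reading gives either 97% or 48%.

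A reader might infer three stronger things:
- **That the figure was certainly written for Objective #4 and misplaced.** The arithmetic and the per-arm wording make this plausible, but other readings share the same noncentrality. If 0.9 is standardised, the SD of 2 also plays no part in the power and only converts the effect to points. The documents do not settle it.
- **That Objective #3 is underpowered.** This holds only if 0.9 means NRS points and the SD of the change is near 2. In units of the SD of the change the power is understated.
- **That expected dropout invalidates the figure.** The 20-success threshold is a feasibility floor, not a planned evaluable number. The plan should say that 20 evaluable patients per arm are assumed; a reduced-completer case is optional in a pilot of this kind.

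**Conclusion.** The concern holds conditionally. With 2 as the SD of the change, the stated 80% does not follow for the paired t-test with n = 20: power is 97% at 0.9 SD or 48% at 0.9 points (two-sided), and the detectable effect is 0.66 SD (1.3 points). One-sided testing does not rescue it (99% and 62%). The figure is right for the paired test only under unstated assumptions: two-sided, a single-visit SD with r near 0.77 (0.9 read as points) or near 0.07 (0.9 read as 1.8 points), or a pooled 40-patient test that the sentence's own wording weighs against. An origin in Objective #4 is a plausible inference and no more.

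Severity is minor. Confidence is high in the conditional failure to reproduce, and lower in where the figure came from. All figures assume 20 evaluable patients per arm.

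**What to change.** Clarify first, then restate.

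1. State the test the figure refers to, whether alpha is one- or two-sided, whether 0.9 is in SD units or NRS points, and whether 2 is the SD of the change or of a single visit. If single-visit, give the assumed correlation and recompute the point values from 2√(2(1 − r)). If a pooled 40-patient test was meant, say so and define each arm's baseline.
2. If 2 is the SD of the change and alpha is two-sided, restate Objective #3: *20 evaluable patients give 80% power to detect a mean change of 0.66 SD (1.3 points), paired t-test, two-sided 5%.*
3. If 0.9 was meant for the between-arm comparison, move it to Objective #4, on the same assumptions: *20 evaluable patients per arm give 80% power to detect a difference of 0.91 SD (1.8 points), two-sample t-test, two-sided 5%.*
4. Say that the figures assume 20 evaluable patients per arm.

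The cost is a few sentences. Enrolment, the planned tests and the feasibility rule do not change.

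### The stated detectable effect of 0.9 counts all 20 enrolled patients per arm as having a day-7 NRS; it is the no-dropout figure and should be labelled and restated for fewer completers

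*Combined protocol and SAP*

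**What the plan says.** Section C.1 sets enrolment: "we plan to enroll 20 patients per arm, with a total of 40 patients for the entire study". Section D.1 adds only this: "This pilot study is based on a convenience sample of 20 subjects per arm". Neither section allows for attrition.

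The power sentence stands in D.2 under Objective #3: "A sample size of 20 per arm will allow us to detect an effect size of 0.9 in the change of dyspnea NRS", for baseline to day 7, "with an 80% power and an alpha of 5%, assuming a standard deviation of 2". The test named in that paragraph is paired: "7 days of dexamethasone will improve dyspnea, respiratory function and quality of life for cancer patients using paired t-tests". The two-arm comparison comes next, under Objective #4: "compared to placebo using two-sample t-tests on the differences between baseline and 4 and 7 days for each outcome measure".

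The Primary Objective paragraph of D.2 counts anyone without a dyspnea NRS at day 7 +/- 2 as a dropout and a feasibility failure. Its decision rule is: "We will declare the study as feasible if we observe at least 20 successes". The rule rests on a departmental review in which "approximately 50% patients completed their interventional clinical trial". Section A.1 gives the working hypothesis as completion of 50% or more.

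The documents give no rule on replacement, over-enrolment or missing data for Objectives #2 to #5.

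**The concern.** The outcome that defines a dropout is the outcome that the day-7 tests need. A patient without a day-7 NRS has no change score to day 7, and so drops out of the paired test in Objective #3 and the two-sample test in Objective #4. The power sentence uses the full enrolment. The feasibility rule, a few lines earlier, would accept a trial in which half of the patients have no such value.

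Section C.1 says that the main goal is to estimate effect sizes for planning a confirmatory trial. A reader who takes 0.9 as the sensitivity of this pilot could give a null day-7 result too much weight, or credit the estimate carried forward with more precision than it has. The documents do not say that the planning figure will be used to interpret results, so this is a risk and not a planned misuse.

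**Working it through.** **Inputs.** Enrolment of 20 per arm, 40 in total (C.1, D.1). Effect 0.9, power 80%, alpha 5%, SD 2 (D.2, Objective #3). Feasibility threshold of 20 completers (D.2, Primary Objective); 20/40 = 50%, an average of 10 per arm. Assumptions: two-sided testing (the plan does not state sidedness) and equal loss in both arms.

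**Formulas.** With n completers per arm and standardised effect d:
- Two-sample t-test: noncentrality d√(n/2), 2n − 2 degrees of freedom.
- Paired t-test within one arm: noncentrality d√n, n − 1 degrees of freedom.
- Power is the probability that the noncentral t exceeds the two-sided 5% critical value. The detectable effect is the d that gives 80% power.

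**Step 1. Reproduce the plan's figure.**
- Normal approximation, two-sample, d = 0.9: n = 2(1.960 + 0.842)²/0.9² = 19.4, rounded up to 20 per arm.
- Exact t, two-sample, n = 20: noncentrality 0.9√10 = 2.846, 38 degrees of freedom, critical value 2.024, power 79.2%. The detectable effect is 0.909 SD, or about 1.8 NRS points at SD 2.

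Other readings do not match:
- One-sided two-sample at 0.9 SD: 87.5% power.
- Paired with 20 patients at 0.9 SD: 96.8% power; detectable effect 0.66 SD.
- 0.9 as raw NRS points (0.9/2 = 0.45 SD): 28% two-sample, 48% paired with 20.
- Paired, 0.9 raw points, all 40 patients pooled: 79.3%. The number agrees, but the sentence says 20 per arm.

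The sentence therefore fits the two-sample comparison of Objective #4, in SD units, with 20 evaluable patients per arm. It stands under a paired test.

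**Step 2. Repeat with fewer completers** (exact t, two-sided 5%).

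| Completers per arm | Two-sample power at 0.9 SD | Two-sample detectable (SD; NRS points at SD 2) | Paired power at 0.9 SD | Paired detectable (SD; NRS points at SD 2) |
|---|---|---|---|---|
| 20 | 79% | 0.91; 1.8 | 97% | 0.66; 1.3 |
| 15 | 66% | 1.06; 2.1 | 90% | 0.78; 1.6 |
| 12 | 56% | 1.20; 2.4 | 81% | 0.89; 1.8 |
| 10 | 48% | 1.32; 2.65 | 72% | 1.00; 2.0 |

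Example, two-sample with n = 10: noncentrality 0.9√5 = 2.012, 18 degrees of freedom, critical value 2.101, power 47.8%. Paired with n = 10: noncentrality 0.9√10 = 2.846, 9 degrees of freedom, critical value 2.262, power 71.7%.

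**Step 3. Check the raw-points reading.** If 0.9 means NRS points, paired power is 48% with 20 patients and 25% with 10. Attrition lowers power on this reading too, but the figure was not met even without dropout.

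**The case against.** A reader might infer that the two statements in D.2 contradict each other. They do not. The power sentence is conditional on 20 per arm, and the feasibility rule is a minimum. If nearly all patients complete, both are satisfied. What is missing is a label on the 0.9 figure.

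A reader might also infer that the plan expects to lose half of its patients. The documents do not say so. The 50% is a completion rate from other departmental trials, for whole trials and not for a day-7 rating, and A.1 uses it as a floor. Retention may well be better: Table 4 allows day 7 by phone within a window of two days either side, and the NRS is collected daily. In the earlier fatigue trial (B.5), dyspnea counts fell from 49 to 43 and from 44 to 38 between days 4 and 8, so 81/93 = 87% remained. That is not retention from baseline, because enrolled numbers are not shown. At a rate like that, about 17 of 20 per arm would complete (0.87 × 20 = 17.4), and two-sample power at 0.9 SD would be 72%. Better retention shrinks the shortfall on that test without removing it.

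Nor can one say that dropouts will not be replaced; the documents are silent.

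The strongest objection concerns the test. Under the paired test that Objective #3 names, 12 completers in an arm still give 81% power at 0.9 SD, so 80% survives a 40% loss (8 of 20). The large shortfall belongs to the two-sample reading. This stands, and it is why the test must be named before the figure is restated.

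Finally, this is a pilot on a convenience sample with a feasibility primary endpoint. The power sentence did not set the sample size, and efficacy is left to a later trial. This limits the consequence but does not make the sentence accurate as written.

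**Conclusion.** The point holds as one of labelling and restatement. The 0.9 figure is true only with no dropout, and D.2 itself does not assume that. At the plan's own benchmark of 50%, about 10 completers per arm, 80% power at 0.9 SD is reached under neither test: 48% two-sample and 72% paired. At 15 per arm, the two-sample test gives 66%, while the paired test gives 90% and is adequate; the paired test falls below 80% only under about 12 completers.

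These figures assume a two-sided 5% level, 0.9 in SD units and equal loss between arms. The point figures in NRS units also take the plan's SD of 2. The result does not show that the trial is too small for its primary purpose, and it does not forecast 50% loss.

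**What to change.** In D.2:
- State which test the figure belongs to (paired within arm, or two-sample between arms), whether testing is two-sided, and whether 0.9 is in SD units or NRS points.
- Label the 20-per-arm figure as the case in which every enrolled patient has a day-7 NRS.
- Restate the detectable effect at 80% power for 10, 15 and 20 day-7 completers per arm. In SD units this is 1.32, 1.06 and 0.91 for the two-sample test, or 1.00, 0.78 and 0.66 for the paired test.

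The cost is a few sentences in the analysis section. No extra patients and no change to study conduct are needed. The downside is that the stated figure becomes less favourable if it belongs to the two-sample test. If it belongs to the paired test, 0.9 is itself not the right figure for 20 patients and would be replaced by the paired values above.

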
Inclusion Criteria
 
 
Diagnosis of cancer
 
Dyspnea with an average intensity level >3/10 on the numeric rating scale over the past week
 
Clinical or radiologic history of lung/pleural involvement (primary or metastatic), lymphangitic carcinomatosis or airway involvement secondary to tumor infiltration
 
Outpatients at MD Anderson Cancer Center seen by the Supportive Care, Rehabilitation Service, Thoracic Oncology or Pulmonary Medicine
 
Able to communicate in English
 
Karnofsky performance status <math>\geq 40\%</math>
 
Age 18 or older
 
Permission from the attending medical oncologist if the patient is currently on an interventional cancer therapy trial.
 
 
Exclusion Criteria
 
 
Delirium (i.e. Memorial delirium rating scale >13)
 
Oxygen saturation <90% despite supplemental oxygen >6L/min
 
Previous allergic reactions to dexamethasone
 
Uncontrolled hyperglycemia as defined by any blood glucose of >300 mg/dl in the past two weeks
 
Severe anemia (Hb <7g/L) not corrected prior to study enrollment (bloodwork is not required if patient did not have recent chemotherapy within last 2 weeks)
 
Post-surgical open wound that has not been healed at the time of enrollment
 
Any infection requiring antibiotics within the past 2 weeks
 
Major surgery within the past 2 weeks
 
Megestrol use at the time of study enrollment
 
Neutropenia (absolute neutrophil count < 1.0) (bloodwork is not required if patient did not have recent chemotherapy within last 2 weeks)
 
Currently on or expected to start cytotoxic chemotherapy within 1 week of study enrollment
 
Chronic obstructive pulmonary disease (COPD) exacerbation at the time of study enrollment
 
Heart failure exacerbation at the time of study enrollment
 
Chronic systemic corticosteroid use (>14 days) at the time of study enrollment
 
Unwilling to provide informed consent
 

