**C.3. Study screening.** A 2 step consent process will be used. A verbal script is provided in the Appendix P. First, a verbal consent will be obtained by the study staff to proceed with screening of potential participants for eligibility and to characterize their dyspnea using the dyspnea survey and the cancer dyspnea scale. Eligible patients will then be formally enrolled onto the study after they have signed the informed consent indicating a willingness to participate in the trial. The number of patients screened, approached, eligible and enrolled will be documented. Reasons for refusal for eligible patients will also be captured.

**C.4. Randomization.** A computer generated sequence in permuted blocks will be used to assign patients to either dexamethasone or placebo via CORE, a secured website. We will stratify by FEV1/FVC ratio (<0.8 vs.  $\geq 0.8$ ). CORE will set up a Randomization website and Investigational Pharmacy personnel will perform the randomization assignment. [name], our research manager, will provide the necessary CORE training for the research team.

**C.5. Blinding.** Both patients and the research staff conducting the assessment will be blinded to the treatment assignment. Placebo capsules identical to dexamethasone 4mg capsules in appearance and taste will be compounded by Green Park Compounding Pharmacy, and both will be dispensed by Investigational Pharmacy at MD Anderson. At the end of the blinded phase, we will assess blinding by asking patients which study arm they believe they have been randomized to.

**C.6. Research staff.** An orientation will be held with research staff involved in this study to introduce them with the study design, and standardize the provision of each intervention.

**C.7. Study Interventions.** The intervention arm will receive dexamethasone 8 mg (2 capsules of 4 mg) given orally twice a day for 4 days, then 4 mg given orally twice a day for 3 days. This dose was chosen partly based on our feasibility data demonstrating that dexamethasone improved dyspnea.

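### Objective #4 compares the arms on change without adjusting for baseline or the FEV1/FVC stratum; adjusting uses data already collected, and its effect on precision runs from a material gain to a small, bounded loss

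*Combined protocol and SAP*

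**What the plan says.** Under Objective #4, section D.2 tests dexamethasone against placebo "using two-sample t-tests on the differences between baseline and 4 and 7 days for each outcome measure". Section 4.0 mentions no covariate, ANCOVA, mixed model or stratified analysis for any objective.

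The design sections supply the material for an adjusted analysis. C.4 states: "We will stratify by FEV1/FVC ratio", with a cut at 0.8, so the stratum is known for every randomised patient. Each change score already needs the baseline value of its outcome.

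C.1 gives the purpose: "The main goal of this study is to determine the effect size for both dexamethasone and placebo arm", as input to a larger confirmatory trial. The size is fixed at a "convenience sample of 20 subjects per arm" (D.1), and C.7 says of the trial: "This study is purely exploratory in nature".

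**The concern.** Objectives #2 and #3 are within-patient comparisons, and Objective #5 sets one arm's blinded week against the other arm's open-label week. Objective #4 is therefore the only concurrent, blinded comparison of the arms, and the only between-arm estimate of that kind the pilot can hand to a later trial.

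A change score fixes the coefficient of baseline at 1. ANCOVA estimates it. Before the cost of estimating covariates, the ANCOVA variance cannot exceed that of the change score, and it may be well below it. In a trial of 40 patients, possibly with many dropouts, the planned interval for the treatment difference could be wider than the data require.

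**Working it through.** **Inputs from the documents.** 20 per arm (D.1). Under Objective #3, D.2 says: "A sample size of 20 per arm will allow us to detect an effect size of 0.9 in the change of dyspnea NRS", with 80% power, alpha 5% and SD 2. The smaller case comes from the feasibility rule in D.2: "We will declare the study as feasible if we observe at least 20 successes". Out of 40 patients, 20 successes would be 10 per arm if split equally.

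**Assumptions.** Two-sided test; SD 2 is the SD of change; 0.9 is in SD units, so the difference is 0.9 × 2 = 1.8 points. Rho and k are not given, so ranges are shown.

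**The plan's own figure.** Two-sample normal approximation: 2 × ((1.960 + 0.842)/0.9)² = 19.4, so 20 per arm, with power 0.812 (0.792 by noncentral t). The figure reproduces as a two-sample calculation. A paired test with n = 20 would have power 0.968 at 0.9 SD. The sentence stands under Objective #3 but fits the Objective #4 test, which is why 1.8 points serves as the benchmark here.

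**Planned t-test.** SE = 2 × √(2/n).
- n = 20: SE 0.632, critical t (38 df) 2.024, 95% CI half-width 1.28, power 79%.
- n = 10: SE 0.894, critical t (18 df) 2.101, half-width 1.88, power 48%.

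**ANCOVA.** Var(ANCOVA)/Var(change) = (1 − rho²)/(1 + k² − 2·rho·k). When k = 1 this is (1 + rho)/2. Its maximum is 1, at k = rho. The average cost of estimating two covariates (baseline and stratum) is 1 + 2/(2n − 5): 1.057 at n = 20 and 1.133 at n = 10. Degrees of freedom are 2n − 4.

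Example, n = 20, rho 0.5, k = 1: variance 4 × 0.75 × 1.057 = 3.17; SE √(3.17 × 2/20) = 0.563; half-width 2.028 × 0.563 = 1.14; power 87.5%.

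Power in %, ANCOVA:

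| | rho 0.3 | rho 0.5 | rho 0.7 | rho 0.9 |
|---|---|---|---|---|
| n = 20 (t-test 79), k = 1 | 92 | 88 | 83 | 79 |
| n = 20, k = 0.8 | 86 | 81 | 78 | 79 |
| n = 20, k = 0.7 | 83 | 79 | 77 | 84 |
| n = 10 (t-test 48), k = 1 | 60 | 54 | 49 | 45 |
| n = 10, k = 0.8 | 52 | 47 | 43 | 45 |
| n = 10, k = 0.7 | 49 | 45 | 43 | 50 |

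The variance ratios in the rho 0.9 column are 1.9/2 = 0.95, 0.19/0.20 = 0.95 and 0.19/0.23 = 0.83. Power recovers at k = 0.7 because k is then well below rho. The low point is at k = rho, not at the smallest k.

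**Interval half-widths, k = 1, rho 0.3/0.5/0.7/0.9.** n = 20: 1.06/1.14/1.22/1.29, against 1.28 for the t-test. n = 10: 1.63/1.75/1.86/1.97, against 1.88.

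**Worst case, k = rho.** n = 20: power 77%, half-width 1.32. n = 10: power 43%, half-width 2.02.

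**Where the gain stops.** With equal SDs, set the two half-widths equal.
- n = 10: (1 + rho)/2 = 1/(1.133 × (2.120/2.101)²) = 0.867, so rho is about 0.73.
- n = 20: (1 + rho)/2 = 1/(1.057 × (2.028/2.024)²) = 0.942, so rho is about 0.88.

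At 10 per arm and rho 0.7, power breaks even at k = 0.976.

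**Simulation.** With balanced, equal, non-prognostic strata (20,000 trials per cell), ANCOVA power was slightly above the formula: for k = 1 and rho 0.3/0.5/0.7, 0.92/0.88/0.85 at n = 20 and 0.62/0.56/0.52 at n = 10. ANCOVA rejected a true null in 4.7% to 5.3% of trials.

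**The case against.** The strongest reply is that nothing is broken. The planned tests are unbiased under randomisation, Objective #4 is secondary, the sample is one of convenience, the study is exploratory, and the decision rule counts completers. All of that stands. It limits the importance of the point but does not remove the possible gain.

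A second reply is that the benefit is least certain where the documents point. D.2 expects about half of patients to complete, which suggests some 10 per arm at day 7. Eligibility for the study requires "Dyspnea with an average intensity level" above 3/10 over the past week, which may make the baseline SD of the dyspnea NRS smaller than its follow-up SD. At 10 per arm with k of 0.8 or 0.7, five of the eight table cells fall below the t-test. This also stands, with two qualifications. The criterion is a weekly average and not the baseline rating itself, so the truncation may be partial. The eligibility list sets no such threshold on FEV1 or quality of life.

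Third, the effect size that C.1 wants for each arm can be read as within-arm change, which this ANCOVA does not sharpen. That reading is open, but the between-arm difference remains the one blinded contrast. Fourth, if 0.9 means NRS points, two-sample power at 20 per arm is only about 30% and every power figure changes; the half-widths do not.

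A reader might infer that the t-test is biased by chance baseline imbalance, or that leaving out the stratum inflates the type I error. Neither follows. Chance imbalance is already part of the t-test's standard error, and ignoring a stratum used in randomisation usually makes the test conservative.

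**Conclusion.** The point holds as one of efficiency. The plan leaves collected baseline information out of its only blinded between-arm estimate. Using it could raise power at 20 per arm by up to about 12 points over the range examined (79% to 92%, or 0.792 to 0.916 unrounded) and narrow the half-width from 1.28 to 1.06. It could also cost up to about 2 power points at 20 per arm, or 5 at 10 per arm.

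A reader might infer that ANCOVA can never do worse, or that a loss needs a baseline SD far below the follow-up SD. The figures support neither: at 10 per arm a loss can occur with equal or nearly equal SDs once rho is about 0.7 or higher. Nor do the documents support a single figure for the gain, since they give neither rho nor k for any outcome. No gain is claimed for the stratum term; it reflects the design and uses one degree of freedom.

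The sizes rest on a change SD of 2, a 1.8-point difference, a two-sided 5% test and equal numbers evaluable per arm. This is a recommended improvement, not a correction of an error, and confidence in its benefit is medium.

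**What to change.** Under Objective #4 in D.2, prespecify for each outcome, at day 4 and at day 7, an ANCOVA with arm, the baseline value of that outcome and the FEV1/FVC stratum (below 0.8, or 0.8 and above). Name the adjusted difference with its 95% CI as the main estimate, and keep the unadjusted two-sample t-test on change as a sensitivity analysis. Naming the main analysis in advance prevents a choice between the two after the results are known.

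The cost is a few lines of SAP text and code and two degrees of freedom, plus the bounded power risk given in the verdict. No new data, visits or patients are needed.
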